#### 7.3.5.2. Analyses for Other Efficacy Endpoints

[REDACTED]

[REDACTED]

[REDACTED]

[REDACTED]

[REDACTED]

[REDACTED]

[REDACTED]

[REDACTED]

### 7.3.6. Analyses of Safety Data

All safety analyses will be performed using the Safety Analysis Set (Section 7.2.6). All safety data collected on or after the first dose of IMP administration up to the last contact after the last dose of IMP, unless specified otherwise, will be summarized by treatment group according to the IMP received. Clinical safety will be addressed by assessing AEs, laboratory assessments, physical examinations, vital signs, and 12-lead ECGs.

#### 7.3.6.1. Extent of Exposure

A subject's extent of exposure to IMP will be generated from the IMP administration page of the CRF. Exposure data will be summarized by treatment group. Duration of exposure to IMP will be expressed as the number of days between the first and last dose of IMP, inclusive, regardless of temporary interruptions in IMP administration and summarized by treatment group.

#### 7.3.6.2. Adverse Events

Clinical and laboratory AEs will be coded using the latest version of the Medical Dictionary for Regulatory Activities. System Organ Class (SOC), High Level Group Term, High-Level Term, Preferred Term, and Lower-Level Term will be attached to the clinical database.

The following AEs will be considered as treatment-emergent AEs (TEAEs):

Any AE with an onset date on or after the start of IMP intake and no later than 30 days after last dose of IMP, or any worsening of any AE on or after the start of IMP intake.

AEs reported before the start of IMP or later than 30 days after the last dose of IMP will be listed.

In addition, summaries and/or listings will be provided for the suspected symptoms/AEs of flare with an onset date on or after the IMP start date until the EoS (including information from Follow-up Visit 2).

Summaries (number and percentage of subjects) of TEAEs per subject by SOC and Preferred Term will be provided by treatment group. TEAEs will also be summarized by causal relationship to IMP and severity. In addition, TEAEs leading to premature discontinuation of IMP will be summarized and listed. Also, all SAEs, including the non-treatment-emergent SAEs, will be listed.

#### 7.3.6.3. Clinical Laboratory Evaluations

Laboratory assessments will be analyzed descriptively. Changes from baseline (Day 1 before IMP intake) and shifts according to normal ranges will be presented as well. Analyses will be done per treatment group.

#### 7.3.6.4. Physical Examinations

Only abnormal post-baseline physical examination results will be listed.

**7.3.6.5. Vital Signs**

Vital signs will be analyzed descriptively. Changes from baseline and shifts according to normal ranges will be presented as well. Analyses will be done per treatment group.

**7.3.6.6. 12-Lead Electrocardiogram**

A descriptive analysis will be done for the 12-lead ECG. Changes from baseline and shifts according to normal ranges will be presented as well. Analyses will be done per treatment group.

[Redacted text block]

**7.3.9. Analysis of Other Assessments**

[Redacted text block]

## **8. DATA MONITORING**

### **8.1. MEDICAL REVIEW**

An independent medical safety review will be implemented for this clinical study. The review will be conducted by an independent blinded clinician experienced in the field of systemic sclerosis. The independent expert will review safety data and assess any potential safety issues arising during the conduct of the clinical study. This process will be described in a separate ‘Independent Medical Safety Review Charter’.

## **9. SAFETY REPORTING**

### **9.1. DEFINITIONS OF ADVERSE EVENTS, SERIOUS ADVERSE EVENTS, AND SPECIAL SITUATIONS**

#### **9.1.1. Adverse Events**

An AE is any untoward medical occurrence, new or worsening of any pre-existing condition, in a clinical study subject administered a medicinal product and which does not necessarily have to have a causal relationship with this treatment.

An AE can therefore be any unfavorable and unintended sign (e.g. an abnormal laboratory finding), symptom, or disease temporally associated with the use of a medicinal product, whether or not considered related. AEs may also include pre- or post-treatment complications that occur as a result of CSP-specified procedures, worsening of the targeted disease, overdose, drug abuse/misuse reports, or occupational exposure. Pre-existing conditions that increase in severity or change in nature during or as a consequence of participation in the clinical study will also be considered AEs.

#### **9.1.2. Serious Adverse Events**

An SAE is defined as an AE that:

- Results in death.
- Is life-threatening (Note: The term ‘life-threatening’ in the definition of ‘serious’ refers to an event in which the subject was at risk of death at the time of the event; it does not refer to an event that hypothetically might have caused death if it were more severe.).
- Requires in-patient hospitalization or prolongation of existing hospitalization.
- Results in persistent or significant disability/incapacity.
- Is a congenital anomaly/birth defect.
- Is medically significant (medical and scientific judgment should be exercised in deciding whether other situations should be considered serious such as important medical events that might not be immediately life-threatening or result in death or hospitalization but might jeopardize the subject or might require intervention to prevent one of the other outcomes listed in the definition above).

### **9.1.3. Unlisted (Unexpected) Adverse Event/Reference Safety Information**

An AE is considered unlisted if the nature or intensity is not consistent with the applicable product reference safety information. For an IMP, the expectedness of an AE will be determined by whether or not it is listed in the reference safety information part of the IB.

### **9.1.4. Adverse Events of Special Interest**

Not applicable.

### **9.1.5. Clinical Laboratory Abnormalities and Other Abnormal Assessments as Adverse Events or Serious Adverse Events**

Laboratory abnormalities without clinical significance based on the investigator's judgment, are not considered AEs or SAEs. However, laboratory abnormalities (e.g. clinical chemistry, hematology, and urinalysis) or other abnormal (clinical study-specific) assessments (e.g. ECG, radiography, vital signs) that require medical or surgical intervention, are associated with signs and/or symptoms, lead to IMP interruption, modification, or discontinuation must be recorded as an AE or SAE if they meet the definition as described in Sections 9.1.1 and 9.1.2, respectively. If the laboratory abnormality is part of a syndrome, the syndrome or diagnosis is to be reported (e.g. anemia instead of decreased hemoglobin).

### **9.1.6. Special Situations**

Special situations are situations that have a possible impact on the safe use of the IMP. These situations might be or might not be associated with AEs.

- Pregnancy
- Abuse or misuse of study drug
  - Abuse of study drug is defined as the persistent or sporadic, intentional excessive use of the study drug, which is accompanied by harmful physical or psychological effects.
  - Misuse of study drug is defined as a situation where the study drug is intentionally and inappropriately used not in accordance with the product information.
- Drug interaction or food interaction with study drug
  - A drug interaction with study drug is defined as a situation in which there is evidence or a suspicion that the study drug interacts with another drug when both are administered together.
  - A food interaction with study drug is defined as a situation in which there is evidence or a suspicion that the study drug interacts with a food when taken together.
- Medication error with study drug

- A medication error with study drug is defined as an unintended failure in the drug treatment process that leads to, or has the potential to lead to, harm to the patient.
- Occupational exposure to study drug
  - Occupational exposure with study drug is defined as an exposure to the study drug as a result of one's professional or non-professional occupation.
- Overdose with study drug
  - An overdose of study drug is defined as the administration of a quantity of the study drug given per administration or cumulatively, which is the intake of more than three tablets/day
- Product complaint or quality defect of study drug
  - Product complaint or quality defect of study drug is defined as complaints or defects of the study drug arising from potential deviations in the manufacture, packaging, or distribution of the study drug.

## 9.2. ASSESSMENT OF ADVERSE EVENTS AND SERIOUS ADVERSE EVENTS

The investigator is responsible for assessing AEs and SAEs for causality and severity. This is the basis for the sponsor's final review and confirmation of accuracy and completeness of event information and causality assessments.

### 9.2.1. Assessment of Causality

The investigator is responsible for assessing the causal relationship to IMP(s) administration or study procedures (e.g. invasive procedures such as venipuncture) based on her/his clinical judgment. The following decision choice will be used by the investigator to describe the causality assessment between the reported event or laboratory test abnormality and the IMP.

- **Unrelated:**  
Time relationship to IMP intake is improbable. Related to other etiologies such as concomitant medications or subject's clinical state.
- **Unlikely:**  
Time relationship to IMP intake is improbable (but not impossible). Concomitant disease or other drugs provide plausible explanations.
- **Possible:**  
Time relationship to IMP intake is reasonable. Event or laboratory test abnormality, could also be explained by disease or other drugs. Information on IMP withdrawal may be lacking or unclear.
- **Probable:**  
Time relationship to IMP intake is reasonable. Unlikely to be attributed to concurrent disease or other drugs. Response to withdrawal is clinically reasonable and rechallenge not required.

– **Certain:**

Time relationship to IMP intake is plausible. Cannot be explained by concomitant disease or other drugs. Response to withdrawal is plausible (pharmacologically, pathologically). Event definitive pharmacologically or phenomenologically (i.e. an objective and specific medical disorder or a recognized pharmacological phenomenon). Rechallenge satisfactory, if ethical and necessary.

It should be emphasized that ineffective treatment (worsening of the disease) should not be considered as causally related in the context of AE reporting.

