### 4.2.2. Clinical Study Design Rationale

This is a randomized, double-blind, parallel-group, placebo-controlled, multi-center, Phase 2a 24-week study in subjects with systemic sclerosis. The randomized double-blind study design was chosen because it is the most rigorous method to generate high-quality scientific data and there is no approved alternative treatment available for comparison. A placebo-controlled study contains internal evidence of assay sensitivity (i.e. when a difference is demonstrated, it is interpretable without reference to external findings), measures absolute safety and efficacy (i.e. it measures the total pharmacologically mediated effect of treatment), is very efficient (i.e. can measure treatment effects with a smaller sample size compared with any other type of controlled study) and minimizes the effect of subject and investigator expectations (ICH E10, 2000). The 2:1 randomization to GLPG1690 avoids unnecessary exposure of subjects to placebo and is typical for Phase 2a studies in systemic sclerosis. The subject eligibility criteria are typical for patient studies in early progressive diffuse cutaneous systemic sclerosis. Based on current European League Against Rheumatism (EULAR) and Scleroderma Clinical Trials Consortium (SCTC) recommendations, background treatment is allowed as defined in Section 4.5.3.2, "Prior and Concomitant Medications". The study duration (24 weeks) was chosen based on experience with previous clinical studies in diffuse systemic sclerosis with a similar mode of action and similar clinical endpoints. The 12-week follow-up period was chosen based on experience with a previous clinical study targeting LPA1 in order to assess the occurrence of flares after IMP discontinuation in subjects with systemic sclerosis compared to placebo.

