#### **5.4.1.4. Treatment Relatedness**

Following ICH-E3 (ICH), the originally reported relatedness to IMP of an AE will be dichotomized as follows:

- *Not IMP related*: all non-missing weaker levels of relatedness than ‘possibly IMP related’.
- *IMP related*: ‘possibly IMP related’ and all stronger levels of relatedness (this class also includes any missing IMP relatedness, as a worst-case consideration).

Only this dichotomized relatedness will be used in tables. Relatedness as originally reported will only be listed.

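### The causality rule on disease worsening makes no exception for flares after IMP is stopped or interrupted, so it pre-judges the relatedness of a risk the follow-up was designed to assess

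*Protocol*

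**What the plan says.** - **Causality rule (Protocol 9.2.1).** The investigator rates each AE "based on her/his clinical judgment" on five levels: unrelated, unlikely, possible, probable, certain. After the five definitions comes the instruction "It should be emphasized that ineffective treatment (worsening of the disease) should not be considered as causally related in the context of AE reporting". No exception is given for worsening after IMP is stopped or interrupted.
- **Purpose of the follow-up (Protocol 4.2.2).** The 12-week period was chosen "in order to assess the occurrence of flares after IMP discontinuation in subjects with systemic sclerosis compared to placebo".
- **What counts as an AE (Protocol 9.1.1).** The definition expressly takes in "worsening of the targeted disease", so a flare is recorded and needs a causality rating.
- **Flare output (Protocol 7.3.6.2).** "summaries and/or listings will be provided for the suspected symptoms/AEs of flare with an onset date on or after the IMP start date", running to end of study and "including information from Follow-up Visit 2". Relatedness is not a condition for inclusion.
- **TEAE window (Protocol 7.3.6.2; SAP 5.4.1.1).** Onset from first IMP intake and "no later than 30 days after last dose of IMP". For subjects entering the extension, the SAP closes the window before the first open-label dose if that comes sooner.
- **Relatedness in tables (SAP 5.4.1.4).** Ratings weaker than possible become not IMP related. Possible or stronger, and any missing rating, become IMP related. "Only this dichotomized relatedness will be used in tables". SAP 5.4.1.8 plans tables of related TEAEs, overall and by severity.

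**The concern.** The protocol names flare after discontinuation as something it wants to learn about, makes sure it is captured as an AE, and then tells investigators how to rate it before they have seen a case. The sentence opens with ineffective treatment, but its bracket equates that with worsening of the disease in general. A flare that follows withdrawal of a drug is a different thing from a drug that does not work, and the text does not separate them.

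Two outputs depend on the rating. One is the set of related-TEAE tables, where a withdrawal effect would be hidden if sites follow the sentence literally. The other is the investigator's causality statement on a serious event, which Section 9.2 makes the basis of the sponsor's own review and which therefore feeds the assessment of suspected unexpected serious reactions under Section 9.4.

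**Working it through.** The plan states no figure on this point, so there is none to reproduce. The check is a comparison of passages and a count of days.

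**Step 1: does the sentence conflict with the scale it follows?** The *possible* category in Section 9.2.1 requires a reasonable time relationship to IMP and accepts that the disease could be an alternative explanation. A flare soon after the last dose can meet both conditions. The closing sentence points the investigator to a lower rating for the same event. The two instructions sit in one section and can give different answers.

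**Step 2: is off-drug worsening within 30 days plausible enough to matter?** Section 2.2.3 gives a terminal half-life of about 11 hours. Section 2.2.4 reports that in the IPF study LPA C18:2 was back to baseline at follow-up, which Section 2.2.2 places 2 weeks after the last intake. Target inhibition can therefore have gone well before day 30. Section 4.5.3.2 also provides for IMP interruptions, so worsening off drug can occur inside the treatment period itself.

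**Step 3: where does a flare appear, and what can the rule change?**

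| Onset of flare | All-TEAE tables | Related-TEAE tables | Flare output | What the rule can change |
|---|---|---|---|---|
| During an interruption, or up to 30 days after last dose | Yes | Only if rated possible or stronger, or rating missing | Yes | Entry to related tables; rating in listings; rating on the SAE form |
| More than 30 days after last dose | No, listed only (SAP 5.4.1.5) | No, whatever the rating | Yes | Rating in listings; rating on the SAE form |

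**Step 4: how much of the follow-up falls in each row?** Follow-up Visit 2 is due 84 ± 7 days after the last dose (Schedule of Activities, Section 6.11). Days outside the TEAE window = visit day − 30.

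- Target: 84 − 30 = 54; 54/84 = 64%.
- Earliest: 77 − 30 = 47; 47/77 = 61%.
- Latest: 91 − 30 = 61; 61/91 = 67%.

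So for roughly the last two thirds of the follow-up, the 30-day window alone keeps a flare out of the related-TEAE tables. The causality rule affects those tables only in the first 30 days after the last dose and during interruptions.

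**Step 5: serious flares.** The SAE form carries a statement of relatedness (Section 9.3.2), with no 30-day limit. If the sentence is followed literally, a serious flare at any time in the reporting period is sent without an investigator suspicion of causality.

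**The case against.** A reader might infer that the rule makes disease worsening never IMP-related, that flares are coded unrelated and cannot appear as related, and that part of the safety endpoint is thereby fixed at zero. The documents do not support this.

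- The subject of the sentence is ineffective treatment. An investigator could fairly say that a withdrawal flare is not that and rate it on the scale, since the rating rests on clinical judgment.
- The sentence names no category. Unlikely fits it as well as unrelated, and a missing rating counts as related.
- The secondary endpoint (Protocol 4.3.2) covers TEAEs, SAEs, AEs and tolerability. It has no relatedness component.
- The flare question is framed as a comparison with placebo, and the flare output in Section 7.3.6.2 runs to end of study whatever the rating. Flares are not lost.
- All SAEs go to the sponsor within 24 hours whether or not thought related (Section 9.3.2), and the sponsor conducts its own review (Section 9.2).
- Subjects who enter the extension have no follow-up visits (Protocol 4.1), so fewer than all randomized subjects will be observed off drug.

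All of this stands, and it limits the consequence. It does not remove the conflict. Clinical judgment is no answer to an emphasized instruction on how to use that judgment, and a sentence that sites can read two ways invites inconsistent ratings in a multi-center study of about 30 subjects, where a few ratings would change a table. The flare output need be no more than a listing, and it does not correct a relatedness rating.

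Nor can one say that the SAP omits a flare analysis. None is visible, but the contents list passes from 5.4.1.9 to 5.4.3 with a gap consistent with blacked-out text.

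**Conclusion.** The point holds in a limited form. Section 9.2.1 makes no exception for worsening after IMP is stopped or interrupted. Read literally, it pre-judges causality for a risk that Section 4.2.2 names, and it conflicts with the definition of *possible* in its own section.

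Two consequences follow from the literal reading. A flare within 30 days of the last dose, or during an interruption, would be tabulated as not IMP related. A serious flare at any time in the reporting period would reach the sponsor without an investigator suspicion of causality. Detection of flares and their comparison between arms are not impaired. For 54 of 84 follow-up days (61% to 67% across the visit window) the related tables would be the same whatever the rating.

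This rests on sites following the sentence as written; the number that would do so is unknown. The number of subjects observed off drug is also unknown. The documents contain no evidence that GLPG1690 causes flares on withdrawal, so no count of misclassified events can be given.

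**What to change.** Reconcile Section 9.2.1 with Sections 4.2.2 and 7.3.6.2. State that the sentence covers only lack of efficacy while the subject is taking IMP, and that worsening with onset after IMP is stopped or interrupted is rated on the existing five-category scale like any other AE. Repeat this in a note in the CRF completion guidelines so that sites apply it alike.

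The relatedness split in SAP 5.4.1.4 can stay as it is. The change would not bring flares starting more than 30 days after the last dose into the related-TEAE tables; those would still be seen only in listings and in the flare output.

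The cost is one protocol sentence and one guideline note, with no new data. The downside is that a few more events may be rated possibly related, in both arms under the blind. No dose, visit or treatment rule changes.

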### 9.2.2. Assessment of Severity

The severity of AEs should be graded using the CTCAE version 5.0. If a CTCAE criterion does not exist, the investigator should use the grade or adjectives: Grade 1 (mild), Grade 2 (moderate), Grade 3 (severe), Grade 4 (life-threatening) or Grade 5 (fatal) to describe the maximum intensity of the AE. For purposes of consistency with the CTCAE, these intensity grades are defined in the table below.

**Table 2 Grading of Adverse Event Severity**

Grade	Adjective	Description
Grade 1	Mild	Asymptomatic or mild symptoms; clinical or diagnostic observations only; intervention not indicated
Grade 2	Moderate	Local or noninvasive intervention indicated; limiting age-appropriate instrumental ADL*
Grade 3	Severe	Severe or medically significant but not immediately life-threatening; hospitalization or prolongation of hospitalization indicated; disabling; limiting self-care ADL**
Grade 4	Life-threatening	Urgent intervention indicated
Grade 5	Death	Death-related AE
* Activities of Daily Living (ADL) Instrumental ADL refer to preparing meals, shopping for groceries or clothes, using the telephone, managing money, etc.		
** Self-care ADL refer to bathing, dressing and undressing, feeding self, using the toilet, taking medications, and not bedridden.		

For AEs associated with laboratory abnormalities, the event should be graded on the basis of the clinical severity in the context of the underlying conditions; this may or may not be in agreement with the grading of the laboratory abnormality. This is upon the investigator's assessment.

If there is a change in intensity (worsening or improvement) of an AE, it must be recorded.

### 9.2.3. Outcome

Each AE must be rated by choosing among:

- Recovered/resolved.
- Recovered/resolved with sequelae.
- Recovering/resolving.
- Not recovered/not resolved.
- Fatal.
- Unknown.

### **9.3. INVESTIGATOR REQUIREMENTS AND INSTRUCTIONS FOR REPORTING ADVERSE EVENTS, SERIOUS ADVERSE EVENTS, PREGNANCIES, AND OTHER SPECIAL SITUATIONS TO THE SPONSOR**

#### **9.3.1. Adverse Events**

The AE reporting period for safety surveillance begins when the subject signs the ICF and ends at the subject's last follow-up visit (the last follow-up visit after the last dose of IMP) as described in the Schedule of Activities (see Section 6.11). In this period, all new AEs, regardless of cause or relationship, derived by spontaneous, unsolicited reports of subjects, by observation and by routine open questioning (such as "How do you feel?") need to be recorded in the source and in the CRF.

In case an AE is ongoing at the time of the last follow-up visit, the investigator needs to follow on the subject until AE resolution or reasonable stabilization and to document in the subject's source documentation. No related updates or additional data on the AE should be reported in the CRF.

If a subject is documented as lost-to-follow-up, ongoing/unknown outcome AEs will not be followed up.

If the AE meets the criteria for seriousness, the SAE form must be completed and sent to the sponsor within 24 hours (see Section 9.3.2).

